7.4 Enrichment

If enrollment to a dose d is stopped early at $n(d) = 3$ or 6 before 7 patients are treated, then the remaining $7 - n(d) = 1$ or 4 patients will be randomized between the remaining two doses. If enrollment to 2 doses is stopped early, then all remaining patients, up to $N_{\text{max}} = 21$, will be treated at the one remaining dose. If enrollment to all 3 doses is stopped early, then the trial will be stopped with no dose selected.

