7.3 Trial Conduct

7.3.1 Dose Assignments

Three dose levels of CYT107 will be considered: 5, 10, and 15 mcg/kg, hereafter denoted as dose levels 1, 2, and 3.

Randomization, rather than conventional sequentially adaptive dose selection, is based on the fact that neither $\text{Pr}(\text{DLT})$ nor any biological outcomes are necessarily monotone increasing in

dose of the biological agent IL-7, and also the scientific goal to obtain unbiased comparisons between doses.

A maximum of 21 patients will be randomized among the three IL-7 doses, with the randomization constrained to have exactly 7 patients per dose. Since 2 patients previously have been enrolled and assigned to d=1, a randomization sequence will be provided for assigning doses to the remaining 19 patients, 3 – 21.

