7.3.2 Within-Dose Safety Monitoring Rule

For each dose $d = 1, 2, 3$, denote $p(d) = \Pr(\text{DLT at dose } d)$. Assume that each $p(d)$ follows a beta(.35, .65) prior. Applying the method of Thall et al.⁴¹, enrollment to dose d will be stopped if $\Pr[p(d) > .35 | \text{data}] > .85$. This criterion will be applied continuously starting at $n = 3$, which implies that accrual to d should be stopped if [number of DLTs] / [number of patients evaluated] is greater than or equal to 3/3 or 4/5. To apply this safety rule for each dose to 2 cohorts of size 3 each may or may not require suspension of accrual. For each dose (a) once 1 or more pats in cohort 1 (pats #1,2,3) have “No toxicity” by day 42 of followup, cohort 2 may begin enrollment, and (b) once 2 or more pats in cohorts 1 and 2 combined (pats #1,2,3,4,5,6) have “No toxicity” by day 42 of follow up, the last patient 7 may be enrolled. This rule has the following operating characteristics.

Operating characteristics of the within-dose safety monitoring rule

True $p(\text{DLT} d)$	$\Pr(\text{Stop accrual to } d)$	Sample Size	Quartiles
.35	.163	7, 7, 7	
.55	.497	4, 7, 7	
.60	.601	4, 6, 7	
.65	.607	3, 4, 7	

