7.7 Summary Reports

The investigator is responsible for completing a toxicity summary report and submitting it to the IND Office, Medical Affairs and Safety Group, for review and approval. This should be submitted after the first, the first three, and the first five evaluable patients per cohort, have completed 42 days post-first CYT107 injection.

A copy of the cohort summary should be placed in the Investigator's Regulatory Binder, under "Sponsor Correspondence".

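### Enrichment can take a dose past 7 patients, but the day-42 accrual conditions, printed boundaries and operating characteristics in 7.3.2 end at patient 7

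*Combined protocol and SAP*

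**What the plan says.** Section 7.3.1 plans 21 patients over three doses, "with the randomization constrained to have exactly 7 patients per dose". Section 7.3.2 gives each dose a DLT probability that "follows a beta(.35, .65) prior" and closes the dose when the posterior probability of a DLT rate above .35 exceeds .85. The check runs continuously from the third patient, and no upper sample size is stated. Two accrual conditions go with it: at least 1 of patients 1-3 free of toxicity at day 42 before patients 4-6 enter, and at least 2 of patients 1-6 "by day 42 of follow up, the last patient 7 may be enrolled". The boundaries printed are 3/3 and 4/5, and the operating-characteristics table shows no sample size above 7.

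Section 7.4 then reassigns the places of a closed dose. After one closure they "will be randomized between the remaining two doses". For two closures the rule is: "If enrollment to 2 doses is stopped early, then all remaining patients, up to" 21 in total, go to the third dose. Section 7.7 asks for toxicity reports to the IND Office "after the first, the first three, and the first five evaluable patients per cohort", with none later.

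**The concern.** Sections 7.3.2 and 7.4 were not fitted together: the first calls patient 7 the last on a dose, while the second allows more. Under 7.1.1 a DLT can be declared up to 42 days after the first injection, so a continuous criterion can act only on patients already assessed. Through patient 7 the two conditions secure some assessed patients before more enter. From patient 8 nothing does.

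Enrichment occurs only when another dose of the same agent has closed for DLTs. The dose that stays open then takes extra patients, without a rule for pacing them and with stopping probabilities that were not calculated for its size. Safety is a primary objective of the trial.

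**Working it through.** **Inputs.** N = 21 and 7 per dose (7.3.1); beta(.35, .65) prior, limit .35, cut-off .85, looks from n = 3, and the table (7.3.2); 42-day DLT window (7.1.1); reassignment (7.4); reports at 1, 3 and 5 (7.7).

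**1. Reproduce the plan's table.** With x DLTs in n patients the posterior is Beta(.35 + x, .65 + n − x). The boundary is the smallest x whose posterior probability above .35 exceeds .85. This gives 3/3, 3/4 (.932), 4/5, 4/6 (.929) and 4/7 (.865). With q = 1 − p, counting the paths that first reach a boundary gives:

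- stop at n = 3: p³
- stop at n = 4: 3p³q
- stop at n = 5: 0, because 4/5 needs 3/4 first
- stop at n = 6: 6p⁴q²
- stop at n = 7: 16p⁴q³

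| True p | Table | Looks at 3-6 | Looks at 3-7 |
|---|---|---|---|
| .35 | .163 | .043 + .084 + .038 = .164 | + .066 = .231 |
| .55 | .497 | .166 + .225 + .111 = .502 | + .133 = .636 |
| .60 | .601 | .216 + .259 + .124 = .600 | + .133 = .732 |
| .65 | .607 | .275 + .288 + .131 = .694 | + .122 = .817 |

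(Sums were taken before rounding.) Looks at 3-6 match the first three rows within .006. The .65 row does not reproduce under this or any other look schedule tried. The table is therefore a calculation for at most 7 patients, with n = 6 as the last look that can save a patient.

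**2. How large a dose can become.**

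- One other dose closed at n = 6: 1 place moves, so some dose reaches 8.
- One closed at n = 3: 4 places move. A dose reaches 7 + 4 = 11 if all go to it; an even split gives 9 and 9.
- Two closed at n = 6: 21 − 6 − 6 = 9. Two closed at n = 3: 21 − 3 − 3 = 15.

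**3. How likely this is.** Suppose the three doses are independent with the same true p. From the plan's own table, the chance that at least one closes is 1 − (1 − .163)³ = .41 at p = .35 and 1 − (1 − .497)³ = .87 at p = .55. It is lower if the true rates are below .35. The 15-patient case needs 3/3 at both other doses, with probability p³ × p³ = p⁶: .002 at p = .35 and .075 at p = .65.

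**4. What the criterion implies past 7.** The boundaries continue as 5/8, 5/9, 6/10, 6/11, 7/12, 7/13, 7/14 and 8/15. The first change comes at once. With 7 as the maximum, 4/7 has no further patient to protect; with an eighth possible it does, which is the right-hand column above. For a 15-patient dose monitored throughout, the stopping probability is .31, .82, .90 and .95 at p = .35, .55, .60 and .65. Given that a dose passes n = 7, it would still close later with probability .11, .50, .62 and .73. Both sets of figures assume that each outcome is known before the next patient enters, which is what no condition secures after patient 7.

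**5. Other pacing text.** Section 4.0 halts accrual between cohorts for 30 days after the last dose, about day 14 + 30 = 44 on three weekly doses. Section 7.4 places enrichment patients in no cohort, so the text does not say whether this halt reaches them.

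**The case against.** The strongest reply is that a safety rule does cover these patients. Under the criterion, "enrollment to dose d will be stopped if" the posterior limit is crossed, at any n from 3 up. Section 7.6 names who applies it. Section 9.0 sends all SAEs to the IND Office within 5 working days, and section 8.0 addresses an unacceptable pattern of toxicity. This stands: a reader might infer that monitoring ends at patient 7, and the documents do not support that. What is missing is pacing, printed boundaries, operating characteristics and scheduled reports.

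Four other tempting readings also fail.

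- **Eight patients enrolled before any reaches day 42.** This would need eight entries on one dose in 42 days, and no accrual rate is given.
- **An enriched dose closed about twice as often as stated.** The figures .31 and .163 at p = .35 suggest this, but .23 of the .31 is stopping by n = 7, and the table never claimed to describe 15 patients. Nor do the 15-patient figures measure the harm of unpaced entry, since they assume known outcomes.
- **The plan presents its day-42 conditions as what makes the criterion workable.** It does not say so. It says only that suspending accrual may or may not be needed, and then lists the conditions.
- **The reporting gap comes from enrichment.** Reports ending at five already miss patients 6 and 7 of an ordinary dose.

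It can also be said that toxicity at one dose need not predict toxicity at another, since 7.3.1 does not assume that DLT risk rises with dose. That tempers the concern but does not remove the need to pace a 42-day endpoint.

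**Conclusion.** The point holds as a gap between 7.3.2 and 7.4. A dose can exceed 7 patients after a single closure, and from patient 8 nothing requires earlier day-42 outcomes to be known before enrolment. Fifteen patients on one dose is possible but rare. The published stopping probabilities do not describe an enriched dose: activating 4/7 alone adds .066 at p = .35 and .133 at p = .55. These sizes rest on the plan's prior and cut-off and on outcomes being known at each look; the chances of enrichment also assume independent doses with equal p. The number of patients exposed without assessment cannot be calculated from the documents. The change is worth making because it is cheap and bears on a primary objective.

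**What to change.** In 7.4, state that a dose receiving more than 7 patients continues under 7.3.2 in groups of at most 3. The next group opens only if the stopping criterion would not be met with every enrolled patient at that dose who lacks a completed day-42 assessment counted as a DLT. On the plan's own criterion this requires:

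- before patient 8: at least 4 of 7 with no DLT by day 42 (boundary 4/7)
- before patient 11: at least 5 of 10 (boundary 6/10)
- before patient 14: at least 7 of 13 (boundary 7/13)

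Print the boundaries 4/7, 5/8, 5/9, 6/10, 6/11, 7/12, 7/13, 7/14 and 8/15. Label the existing table as applying to a maximum of 7, recheck its .65 row (.607 stated, .694 recomputed), and add operating characteristics for enriched sizes such as 8, 9, 11 and 15, computed with the gates as applied. Extend 7.7 with a report at patient 7 and after each further group. Reconcile the between-cohort halt in section 4.0 with enrichment.

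Two nearby passages can be aligned in the same edit. Section 7.4 names closures only at n = 3 or 6, although 3/4 also meets the criterion. The condition before patient 7 is satisfied with 4 DLTs in 6, although 4/6 meets the criterion too.

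The cost is protocol wording, one recalculated table and a few short reports. Accrual slows by about 42 days per group, and only after another dose has closed for toxicity.

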7.5 Data Analysis

7.5.1 Tabulation

Each primary and secondary variable will be tabulated by dose using summary statistics, consisting of counts and percentages for categorical variables and the sample median and range for numerical valued variables. Kaplan-Meier plots³⁴ will be used to estimate the PFS and OS distribution for each dose.

7.5.2 Regression Modeling

Bayesian longitudinal regression models⁴² will be fit to the final data on each of the four biological response variables, as defined in section 1, including in each model a parametric function of time and the baseline covariates patient age, type of graft, and disease (AML vs MDS). Preliminary analyses will include a smoothed plot of each longitudinal outcome variable as a function of time.

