7.0 Statistical Considerations

7.1 Outcomes and Covariates

7.1.1 Primary Outcomes

Toxicity. Dose limiting toxicity (DLT) is defined as any of the following events: grade 3 or 4 GVHD, secondary graft failure, disease relapse, development of PTLD, development of PML, grade 2 organ failure or grade 2-4 skin rash, fatigue, AST and ALT elevations, allergic anaphylaxis, or hemolytic anemia, attributable to CYT107, or death, occurring within 42 days of the first CYT107 injection.

Biological Responses. The absolute number and percentage of total White Blood Cells (WBCs) consisting of T-cells and of B-cells will be observed at 1, 3, 6, 9 and 12 months.

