7.5.3 Optimal Biological Dose Selection

At the completion of the trial, when all patients have been followed up fully and all outcomes evaluated, the optimum biological dose (OBD) will be defined as the dose maximizing the sample mean percentage of WBCs that are T-cells, evaluated at one year of follow up.

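### The longitudinal models of biological response in 7.5.2 state no dose term, so as listed they cannot estimate the comparison between doses for which the trial randomises

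*Combined protocol and SAP*

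**What the plan says.** The biological part of the primary outcome is defined in 7.1.1: "The absolute number and percentage of total White Blood Cells (WBCs) consisting of T-cells and of B-cells will be observed". The planned visits are months 1, 3, 6, 9 and 12, which makes four variables at five times.

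Section 7.5.2 says that Bayesian longitudinal regression models "will be fit to the final data on each of the four biological response variables, as defined in section 1". (The four variables are in fact defined in 7.1.1, so that cross-reference needs correcting.) The content of each model is given as "including in each model a parametric function of time and the baseline covariates patient age, type of graft, and disease (AML vs MDS"). The exploratory step is likewise by time alone: "Preliminary analyses will include a smoothed plot of each longitudinal outcome variable as a function of time".

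Dose enters the analysis of these outcomes in two other places. Section 7.5.1 has every primary and secondary variable summarised by dose, with medians and ranges for numerical variables. In 7.5.3, "the optimum biological dose (OBD) will be defined as the dose maximizing the sample mean percentage of WBCs that are T-cells" at one year.

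On design, 7.3.1 states: "A maximum of 21 patients will be randomized among the three IL-7 doses, with the randomization constrained to have exactly 7 patients per dose". It gives two reasons for randomising: DLT probability and biological response need not rise with dose, and "the scientific goal to obtain unbiased comparisons between doses" is wanted.

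**The concern.** The randomised factor is missing from the stated terms of the only model planned for the primary biological response. A model without dose can describe how T and B cells recover after treatment, but it has no parameter for how recovery differs between doses.

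What is lost is the adjusted comparison and its uncertainty. Section 7.5.2 names graft type, age and disease as covariates for these outcomes, but no planned comparison of doses uses them. With at most 7 patients per dose, chance differences in case mix are likely. The comparison is also not fully randomised: "Since 2 patients previously have been enrolled and assigned to d=1". Neither the tables nor the selection rule comes with an interval or a probability that the chosen dose is best, so a reader of the final report could not tell a clear winner from a near tie.

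If dose is added only after the data are seen, its form (linear or categorical, with or without an interaction with time) becomes a post hoc choice. The form matters because 7.3.1 declines to assume monotonicity.

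**Working it through.** The plan gives no effect size, SD, power or precision for the biological outcomes, so there is no stated figure to reproduce. The check has three parts.

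**1. The sections side by side.**

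| Section | Role of dose | Covariates | Uncertainty |
|---|---|---|---|
| 7.2 (baseline covariates) | not listed | – | – |
| 7.5.1 (tables) | summaries by dose | none | range only |
| 7.5.2 (models) | not stated | age, graft type, disease | available, but not for dose |
| 7.5.3 (dose selection) | raw one-year means ranked | none | none stated |

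No other section models these outcomes. With only the listed terms, the fitted value for given time, age, graft and disease is the same at all three doses. As an illustration, one data set was simulated with 21 patients, 7 per dose, five visits, and a built-in step of 10 points per dose level. The fitted 12-month means were 39.99, 39.99 and 39.99 without a dose term, and 29.27, 41.80 and 51.35 with a dose factor.

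**2. Precision of a dose contrast.** With 7 per dose (7.3.1) and one time point, the 95% half-width for a difference between two doses is 1.96 × √(2/7) = 1.05 SD (normal approximation). Two-sided 5% power is about Φ(δ√(7/2) − 1.96), which gives about 15%, 46%, 80% and 96% for assumed differences δ of 0.5, 1.0, 1.5 and 2.0 SD.

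**3. What a dose term would do for dose selection at month 12.** Assumptions: 7 per dose, normal outcome, one dose 0.5 SD better than two equal others, complete data, equal within-patient correlation ρ between visits, no covariate adjustment, and priors too weak to matter.

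The probability of picking the best dose is P = ∫ φ(z − k) Φ(z)² dz, with k = 0.5√7 / f = 1.323 / f. Here f is the SD of the estimated dose mean relative to that of the raw one-visit mean: f² = ρ + (1 − ρ)h, where h is the leverage of the estimate under the chosen time curve. The visits at 1, 3, 6, 9 and 12 months have mean 6.2 and sum of squares 78.8.

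At ρ = .5:

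| Estimate used to rank doses | h | f | P(best dose picked) |
|---|---|---|---|
| Raw month-12 mean | 1 | 1 | 72% |
| Dose × categorical time | 1 | 1 | 72% |
| Dose × quadratic time | .909 | .977 | 73% |
| Dose × linear time | 1/5 + 5.8²/78.8 = .627 | .902 | 76% |
| Constant dose effect, all five visits averaged | 1/5 | .775 | 81% |

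At ρ = .3 and .7 the linear-time figures are 77% and 74%, and the constant-effect figures are 86% and 77%. If only 5 or 4 patients per dose are measured at one year, the raw mean picks the best dose 67% or 63% of the time.

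**The case against.** **Dose may be implied.** The word that introduces the list need not make it exhaustive, and dose is a design factor rather than a baseline covariate. This may be a drafting gap, so the accurate statement is that no dose term is stated. The omission still matters: the text goes down to the AML-versus-MDS contrast and leaves the randomised factor and its form open.

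**Doses are compared elsewhere, and no decision rests on 7.5.2.** This stands. A reader might infer that the trial never compares doses, or compares them at one time only. The documents do not support that: 7.5.1 summarises every primary variable by dose, and those variables are measured at five times. Assignment, the safety rule and the choice of optimal dose would all run unchanged if 7.5.2 stayed as it is.

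**The model might add little to selection.** This largely stands. A reader might infer that using all visits raises correct selection from 72% to 81%. That figure needs a dose effect that is constant over all five visits and averaged across them. A dose-by-time model read at month 12 does not deliver it, even when the effect is truly sustained. A parametric curve of the wrong shape can also bias the month-12 value.

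**Graft imbalance.** A reader might infer that the raw means are biased by graft type. The documents give neither the graft mix nor an effect of graft type on T-cell percentage. If 10 of 21 patients had cord grafts (an assumption), some pair of doses would differ by 3 or more cord patients with probability 42%, and a given pair with probability 19%. Among randomised patients, chance imbalance adds variance and does not by itself bias the means. Section 7.5.2 lists graft type as a covariate but does not say that adjustment is necessary.

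**Conclusion.** The point holds in a limited form. As listed, the only planned models of the primary biological response cannot estimate the dose comparison that 7.3.1 gives as a reason for randomising. What remains is descriptive, unadjusted and without stated uncertainty.

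The gain from adding dose is mainly an adjusted contrast with an interval. The improvement in correct selection at month 12 is about 0 to 4 percentage points over 72% at ρ = .5. It rests on the assumed 0.5 SD advantage, 7 complete patients per dose and equal correlation between visits. Even with a dose term, only differences of roughly 1.5 SD or more would be shown with 80% power.

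The documents do not support the further step that the raw-mean rule in 7.5.3 must be replaced by a model-based ranking. That is a separate design preference.

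**What to change.** In 7.5.2, before the final data are analysed:

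- Add dose to each model as a three-level categorical factor, so that no monotonicity is assumed, with a dose-by-time term and a patient-level random effect. State the form of the time function and the priors, because both carry weight with 21 patients.
- Report the adjusted posterior dose contrasts at 12 months with credible intervals, and the posterior probability that each dose is best.
- Draw the preliminary smoothed plots by dose.
- Point the definition of the four variables to 7.1.1.

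In 7.5.3, keep the raw-mean rule and add that the model-based contrasts will be shown beside it as support.

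The cost is a few lines of SAP wording and a little more analysis work, with no new patients or measurements. The downside is that intervals will be wide with 7 patients per dose. The report should say so rather than present the selected dose as clearly superior.

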4.0 Treatment Plan and Study Design

CYT107 will not be administered before Day 60 but could be started as late as Day 180 post-CBT or haplo-SCT.

The active treatment period will be from the first injection of CYT107 and for 30 days after the last injection. The follow-up period will be for three years after the last injection.

Patients will be treated with CYT107 by intramuscular route (I.M.)* post CBT or haplo-SCT (from 60 to 180 days), with 1 of 3 doses below:

- 5 mcg/kg/dose for 3 doses, one week apart
- 10 mcg/kg/dose for 3 doses, one week apart
- 20 mcg/kg/dose for 3 doses, one week apart

Enrollment of the first 3 participants will be staggered by 14 days. Accrual in between cohorts will be halted for 30 days after the last patient in each cohort has received the last dose of CYT107.

* If the patient's platelet count is below 35,000, the product may be administered by subcutaneous route.

All patients will receive foscarnet for the management of CMV infection as per Stem Cell Transplantation and Cellular Therapy Department's standard of care.

Dose modifications

Treatment will be permanently discontinued for patients developing grade 3 or 4 GVHD, secondary graft failure, disease relapse, PTLD, PML, grade 2-4 skin rash, or grade 3-4 non-hematological toxicity attributable to CYT107.

Patients who develop grade 2 non-hematological toxicity attributable to the CYT107 will have the next dose withheld until the toxicity resolves to grade 1. If the toxicity resolves within 2 weeks the drug will be administered at the same dose, however if the toxicity takes more than 2 weeks to resolve the drug will be administered at the next lower level, or permanently discontinued if the patient was already at the lowest level. If the toxicity takes more than 4 weeks to improve to grade 1, the CYT107 will be permanently discontinued

For patients who at study entry have grade 0, 1 or 2 hematological toxicity and develop grade IV hematological toxicity attributable to the CYT107 will have the next dose withheld until the toxicity resolves to grade 2. If the toxicity resolves within 2 weeks the drug will be administered at the same dose, however if the toxicity takes more than 2 weeks to resolve the drug will be administered at the next lower level, or permanently discontinued if the patient was already at the lowest level. If the toxicity takes more than 4 weeks to improve to grade 2, the CYT107 will be permanently discontinued

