6.4 Correlative Studies

Circulating lymphocyte subsets will be measured, using immune reconstitution lab, prior to administration of each dose of CYT107 and approximately days 21 and 28, and 100 days after the first injection in the MD Anderson CLIA-approved clinical flow cytometry laboratory. The lymphocytes subsets analyzed will be CD4 and CD8 subsets including naïve and memory T-cells based on expression CD45RO, CD62L and CCR7. T-regulatory cells, B-cells and NK cells will also be evaluated. This studies will be used to help identify the optimal IL-7 dose for a subsequent phase-II trial.

Correlative study samples will be obtained via MD Anderson laboratory protocol LAB99-062 if patient consents.

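### The comparison that selects the OBD ignores the pre-dose T-cell value and the days from transplant to first injection; with 7 patients per arm it probably loses precision and is exposed to baseline imbalance

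*Combined protocol and SAP*

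**What the plan says.** - **Models.** Section 7.5.2 fits Bayesian longitudinal models to the four biological responses, "including in each model a parametric function of time and the baseline covariates patient age, type of graft, and disease (AML vs MDS"). Dose is not named as a term.
- **OBD rule.** Section 7.5.3 defines the OBD as "the dose maximizing the sample mean percentage of WBCs that are T-cells, evaluated at one year of follow up". The rule does not refer to the 7.5.2 models.
- **Responses.** Under section 7.1.1 they "will be observed at 1, 3, 6, 9 and 12 months", so the pre-dose value is not part of the outcome series either.
- **Pre-dose measurement.** Section 6.4 measures lymphocyte subsets "prior to administration of each dose of CYT107".
- **Start of treatment.** Section 4.0: "CYT107 will not be administered before Day 60 but could be started as late as Day 180".
- **Covariate list.** Section 7.2 contains neither the pre-dose T-cell level nor the days from transplant to first injection. Its engraftment times are different quantities.
- **Allocation.** Section 7.3.1: "A maximum of 21 patients will be randomized among the three IL-7 doses, with the randomization constrained to have exactly 7 patients per dose". It adds: "Since 2 patients previously have been enrolled and assigned to d=1".

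**The concern.** The baseline value of an outcome is usually among its better predictors, and the plan's own background (section 2.3) shows T cells recovering with time since transplant. A patient first injected near day 180 is at a different point of that recovery from one injected at day 60. The models instead adjust for age, graft type and disease.

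In arms of 7, differences between arms in baseline T cells or start day are likely and would be carried into a raw-mean comparison. Randomization makes such differences a matter of chance for 19 patients. It gives no such assurance for the 2 patients already placed at dose level 1, although section 7.3.1 gives unbiased comparison between doses as a reason for randomizing. At stake is which dose goes forward to phase II.

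**Working it through.** **The plan's own figure.** 3 × 7 = 21 and 2 + 19 = 21, so the sample size is consistent. The documents give no power, SD, effect size or precision target for the OBD comparison, so there is nothing further to reproduce.

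**Likely imbalance.**
- Start day, assumed uniform on 60–180: SD = 120/√12 = 34.6 days. The SE of a difference between two arm means is 34.6 × √(2/7) = 18.5 days. The chance that two given arms differ by more than 20 days is .28. By simulation, the chance that the largest of the three gaps exceeds 20 days is .53.
- Baseline T-cell level, assumed normal: SE of a two-arm difference = √(2/7) = 0.53 SD. By simulation, the chance that the largest gap exceeds 0.5 SD is .62.

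**Precision of a dose difference, adjusted versus raw.** With N patients, K = 3 arms and q covariates that explain a share R² of the within-arm variance:

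variance ratio = (1 − R²) × [1 + q/(N − K − q − 1)]

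The bracket is the cost of estimating the slopes. For N = 21 it is 1 + 1/16 = 1.0625 with one covariate and 1 + 2/15 = 1.133 with two. The documents give no correlation between the pre-dose value and the one-year T-cell percentage, so R² = ρ² is shown over an assumed range. The chance of choosing the right dose was simulated by least squares with 7 patients per arm and one dose better by 0.5 SD; the raw-mean rule gives .72.

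| Assumed ρ (baseline value) | Baseline only: ratio | P(correct) | Baseline plus uninformative start day: ratio | P(correct) |
|---|---|---|---|---|
| 0 | 1.06 | .71 | 1.13 | .70 |
| .3 | .91 × 1.0625 = .97 | .73 | .91 × 1.133 = 1.03 | .72 |
| .5 | .75 × 1.0625 = .80 | .76 | .75 × 1.133 = .85 | .75 |
| .7 | .51 × 1.0625 = .54 | .83 | .51 × 1.133 = .58 | .82 |

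**Break-even.** 1 − 1/1.0625 = .06 for one covariate and 1 − 1/1.133 = .12 for two. If both are added to a model that already holds three covariates (one parameter each), the cost is (1 + 5/12)/(1 + 3/14) = 1.17, and break-even is R² = .14. If only 15 patients have one-year values, the break-even points for one and two covariates rise to .09 and .18, and to .25 when two are added to three.

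**The case against.** **The gain is not assured.** A reader might infer that the plan certainly wastes precision, taking 1 − ρ² (.91, .75, .51) as the variance factor and .74, .77 and .84 as the chance of a correct choice. That treats the slopes as known. With two slopes estimated from 21 patients there is no gain at ρ = .3, and a small loss if both covariates are uninformative. This objection stands, and it is why the baseline value comes first and start day takes second place.

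**The drift evidence is indirect.** Section 2.3 reports median CD4 rising from 4 to 22 and CD8 from 6 to 11 (×10⁶/L) between days 30 and 100. A reader might take this as the size of the start-day effect. It is not: these are absolute counts, not a percentage of WBCs, after double cord blood transplant only, and they mostly precede the dosing window. Counted from first injection, the OBD is read at about day 425 to 545 after transplant (60 + 365 to 180 + 365). The documents show no comparable drift there. Start day probably matters more at month 1 than at one year.

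**The baseline may not be in hand for everyone.** Correlative samples depend on consent (6.4), and missed ones are tolerated (6.0). The pre-treatment list in 6.1 names no blood count, so a baseline expressed as a percentage of WBCs is not assured. This stands and shapes the fix.

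**Imbalance is not a second penalty.** Among the 19 randomized patients, chance imbalance is sampling error already contained in the .72. Only the 2 non-randomized patients add a possible bias, of unknown size and direction.

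**Time might be counted from transplant.** The origin in 7.5.2 is unstated, and 7.1.2 fixes it only for time-to-event outcomes. A transplant origin would carry part of the start-day effect. It would also place the month-1 response before any drug, since dosing cannot begin before day 60, so this reading is weak.

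**Conclusion.** The omission is clear from sections 7.2, 7.5.2 and 7.5.3, and the change is worth making. The pre-dose value is the main item and 7.5.3 is the place where it counts.

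The likely benefit is modest to useful. For the baseline value alone, the variance of a dose difference changes by a factor of .97 to .54, and the chance of choosing the right dose goes from .72 to .73–.83. Against that, variance rises by about 6% (one covariate) or 13% (two) if the covariates carry no information, and the chance of a correct choice falls to about .71 or .70.

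These figures rest on an assumed correlation of .3 to .7, a 0.5 SD advantage for one dose, and complete one-year data on 21 patients. The documents do not support saying that precision is certainly lost, or that start day is known to distort the one-year comparison.

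**What to change.** 1. In 7.5.2, name dose as a term and add the pre-dose-1 value of each response as a covariate.
2. Add days from transplant to first injection with a shrinkage prior, which fits the Bayesian models already planned, or prespecify it as a sensitivity analysis. State the origin of the time function.
3. List both variables in 7.2, and obtain a blood count with differential before the first dose so that the baseline is available as a percentage of WBCs.
4. Keep patients with a missing baseline in the model, for example by Bayesian imputation, since dropping them would shrink arms of 7.
5. In 7.5.3, base the OBD on model-adjusted one-year dose means and report the raw means alongside. Changing 7.5.2 alone would leave the dose choice untouched.

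The cost is revised wording in four sections (6.1, 7.2, 7.5.2 and 7.5.3), one pre-dose blood count where it is not already done, and one or two more parameters per model. It should be fixed before outcomes by dose are examined, so that covariates are not chosen after the fact in a 21-patient trial.
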